## **Study protocol:**

### **(1) Experimental: prolonged intravenous infusion of $\beta$ -lactams Antibiotics**

Administer according to the PK/PD optimized regimen with the goal of increasing  $T > MIC$ . (1)

Carbapenems: Calculate the daily dose according to the creatinine clearance rate and divide it into 3 times. Each time, the dose is injected intravenously at 1/2 dose for 15 minutes, and the remaining 1/2 dose is injected at a constant rate for 3 hours. (2) Cephalosporins: calculate the allowable daily dose according to the creatinine clearance rate, inject at a uniform rate within 24 hours. (3)  $\beta$ -lactams and  $\beta$ -lactamase inhibitor compound: the daily dose is calculated according to the creatinine clearance rate and injected at a uniform rate within 24 hours.

### **(2) No Intervention: short-term intravenous infusion of $\beta$ -lactams Antibiotics:**

The daily allowable dose is calculated according to the creatinine clearance rate. The carbapenems, cephalosporins and  $\beta$ -lactamase inhibitor compound preparations are administered in accordance with the dosage and usage required by the instructions, and the injection is generally 30 minutes.

Timetable :

Each research center is divided into 3 research phases, and the first 4 weeks of each research phase is the wash-out period. 12 weeks is a research phase, and they are randomly assigned to the participating centers of the prolonged intravenous infusion of  $\beta$ -lactams Antibiotics group. All infected patients admitted after the start of the research phase are subjected to a prolonged intravenous infusion of  $\beta$ -lactams Antibiotics regimen; and the other centers randomly assigned to enter the short-term intravenous infusion group. The participating centers will implement a routine 30-minute infusion program for all infected patients admitted after the start of the research phase.

After the 12-week study period and a 4-week wash-out period is over, the newly admitted cases will be administered according to the method of the next study period. After the 4-week wash-out period is over, it enters the second research phase. In the second research phase, each participating center automatically crosses into another program group, that is, the unit that executes the prolonged intravenous infusion of  $\beta$ -lactams Antibiotics program in the first phase automatically executes the conventional short-term intravenous infusion program, and vice versa. The participation period of each center is at least one year, in order to cover the difference in the incidence of different pathogenic infections in different seasons throughout the year.

Patients who had been admitted to the hospital and started taking medication before the start of this study were still taking medication according to the original schedule during the washout period and were not included in this study. The dosing regimen of all enrolled cases is based on the group of the research center on the day of enrollment, and the regimen must be strictly implemented until the end of the treatment, regardless of whether the antibiotic treatment of the case crosses the research phase. The researcher should ensure the completeness and authenticity of the research data record.

### **Statistical analysis plan:**

- (1) Statistical software: All statistical analysis is mainly conducted by SAS 9.4 and R 3.6.0.
- (2)
  - 1) Full analysis set (FAS): includes cases that have been randomly assigned to the group, have used the study medication at least once, and have follow-up records.
  - 2) Per-Protocol set (PPS): it is a subset of the ITT data set, that is, all those who complete relevant observations according to the requirements of the plan and meet the following conditions, refer to those whose compliance is between 80% and 120%, Did not seriously violate the research plan, completed all the visits, and completed the CRF, the main evaluation indicators and most other evaluation indicators are not missing.
  - 3) Safety set (SS): All groups who have been randomized and used study drugs at least once constitute the safety set of this study. All safety information records from the subjects will be evaluated, including adverse events, serious adverse events, and abnormal changes in safety indicators that have clinical significance.
  - 4) The efficacy indicators were analyzed by FAS and PPS population respectively. Safety analysis adopts SS population analysis.
  - 5) Stratified analysis: According to the subject's SOFA score (2-7 points; 8 -13 points), stratified analysis is carried out on the 28-day survival rate, and PK/PD-guided optimized antibiotic regimens are explored for their related effects on the prognosis of patients with toxicosis.
- (3) Statistical analysis content
  - Statistical analysis content
    - 1). General principles of statistical analysis

All statistical tests use two-sided tests. After P value is adjusted by FDT, Q value  $\leq 0.05$  will be considered as statistically significant (unless otherwise specified). The description of quantitative indicators will calculate the mean, standard deviation, median, minimum, maximum, lower quartile (Q1), upper quartile (Q3), and classification indicators to describe the number of cases and percentages of each category. The general comparison of the two groups will be analyzed by appropriate methods according to the types of indicators. The comparison of quantitative data between groups will be based on the data distribution using group t test (homogeneity of variance, normal distribution) or Wilcoxon rank sum test, classification The data uses the chi-square test or the exact probability method (if the chi-square test is not applicable), and the rank data uses the Wilcoxon rank sum test or the CMH test. Kaplan–Meier description, Log-rank test and Cox regression were used for the survival time data of the study subjects. The research results of each research center are evaluated by meta-analysis to evaluate the heterogeneity and the overall research merger effect. The potential confounding bias (treatment, service, management, etc.) of each research center is analyzed using a multi-layered mixed model.

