## 3). Effectiveness analysis

(1) Baseline index: Describe the baseline of each curative effect index, refer to general statistical methods for the comparison method between groups. A stratified analysis was performed

based on the subjects' SOFA score.

(2) Main efficacy indicators: The clinical efficacy is evaluated by the survival rate in the ICU and the survival rate on the 28th day after enrollment. Simultaneous FAS analysis and PPS analysis.

(3) Secondary curative effect index

- ① Stratified analysis of clinical effectiveness;
- ② Bacterial clearance rate;
- ③ Infection recurrence rate;
- ④ Isolation rate of new resistant bacteria;
- ⑤ Infection rate of newly emerging drug-resistant bacteria;
- ⑥ Total cost of living in ICU;
- ⑦ Total hospitalization expenses;
- ⑧ DDD is used for antibiotics in hospital.

For all the outcome indicators, first conduct independent evaluation in each research center in accordance with general principles. Then meta-analyze the research results of each research center. Assess the heterogeneity and the combined effect of the overall study. Finally, a multivariate stratified mixed model was used to adjust the potential bias.

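### The per-protocol set requires all visits to be completed with no exception for death, yet survival is analysed in it, so read literally the primary event removes patients.

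*Protocol*

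**What the plan says.** Under the heading Statistical analysis plan, item (2) 2), the Protocol defines the PPS as "all those who complete relevant observations according to the requirements of the plan and meet the following conditions". The conditions are compliance between 80% and 120%, no serious violation of the plan, and that the patient "completed all the visits, and completed the CRF, the main evaluation indicators and most other evaluation indicators are not missing". Completing the visits and having the main indicators recorded are two separate requirements. Death is not mentioned in this definition, and no other part of the document makes an exception for it.

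Item (2) 1) sets a looser condition for the FAS: patients must have been randomly assigned, "have used the study medication at least once, and have follow-up records". It has no visit-completion rule.

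Item (2) 4) states: "The efficacy indicators were analyzed by FAS and PPS population respectively". Section 3). Effectiveness analysis, item (2), names the main indicators: "The clinical efficacy is evaluated by the survival rate in the ICU and the survival rate on the 28th day after enrollment". It then calls for "Simultaneous FAS analysis and PPS analysis". Section 1). General principles adds that "Log-rank test and Cox regression were used for the survival time data of the study subjects". The document does not rank the two sets or call the PPS analysis supportive.

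**The concern.** A patient who has died has a known survival outcome, so the requirement that main indicators be recorded is met. The visit requirement is not met, because no visit can be attended after death. Applied as written, the rule makes membership of the PPS depend on the outcome that the PPS is used to estimate.

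Survival in the PPS would then be overstated in both arms and the absolute difference between arms reduced. In the extreme there would be no deaths left to analyse. A PPS result of that kind, reported beside the FAS result with equal standing, could be taken for a lack of effect among treated-as-planned patients when it only reflects who was removed. If the point is left to data review, membership of the PPS for each death would be settled when outcomes are known.

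**Working it through.** The Protocol states no mortality, sample size or visit schedule, so there is no figure of its own to reproduce. The check has two parts.

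**Reading the rule**

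| Condition for the PPS | Can a patient who died early meet it? |
|---|---|
| Main indicators not missing | Yes, survival status is known |
| All visits completed, read literally | No, unless every visit came before death |
| All visits completed, read as those due while alive | Yes |

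Both readings are open. The phrase "complete relevant observations according to the requirements of the plan" leans towards the second, since a plan cannot require visits after death, but it does not state it.

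**Effect on 28-day survival**

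Let *s* be true survival in an arm and *e* the share of day-28 deaths that the visit rule excludes, with all survivors retained. Then

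PPS survival = s / (s + (1 − s)(1 − e)).

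Two bounds need no mortality figure:

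- e = 0 (visits due while alive): PPS survival = s. No bias.
- e = 1 (literal reading, with a visit at or after day 28): PPS survival = s/s = 100% in each arm, difference 0. The log-rank and Cox analyses have no deaths up to day 28 in this set.

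To show what e = 1 does to the set, assume survival of 70% v 75%. Of every 1000 patients per arm, 700 v 750 remain with 0 deaths, against 300 v 250 deaths in full.

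Between the bounds, take e = 0.5 in both arms. The survival rates and this value of e are assumptions, used only for illustration:

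| Assumed true survival | True difference | PPS survival | PPS difference | Survival odds ratio, true and PPS |
|---|---|---|---|---|
| 60% v 65% | 5.0 points | 0.60/0.80 = 75.0% v 0.65/0.825 = 78.8% | 3.8 points | 1.24 |
| 70% v 75% | 5.0 points | 0.70/0.85 = 82.4% v 0.75/0.875 = 85.7% | 3.4 points | 1.29 |
| 80% v 85% | 5.0 points | 0.80/0.90 = 88.9% v 0.85/0.925 = 91.9% | 3.0 points | 1.42 |

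If e is 0.9, the three differences fall to 1.1, 0.9 and 0.7 points.

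The odds ratio is unchanged because the PPS odds of survival are s / ((1 − s)(1 − e)), and an equal e below 1 cancels between arms. With unequal shares e₁ (prolonged infusion) and e₀ (short infusion), the odds ratio is multiplied by (1 − e₀)/(1 − e₁), so it is biased as soon as the two shares differ, for example because deaths come at different times in the two arms.

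**ICU survival.** The 100% v 100% bound applies to day 28 only. A patient who attends the last visit and later dies in the ICU stays in the PPS as an ICU death. For this indicator the literal rule removes deaths before the last visit and keeps those after it.

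**The case against.** The best defence is that the literal reading defeats the document's own purpose. The Protocol orders a survival analysis in the PPS, so a rule that could empty that set of day-28 deaths is unlikely to be what the sponsor meant. With no visit schedule in the document, the visits might also be status checks that a recorded death satisfies. Membership details of this kind are often settled in a separate statistical analysis plan or at data review. The intermediate figures rest on assumed mortality and an assumed share of exclusions, and with equal exclusion the odds ratio does not move. The FAS analysis runs alongside, and because section 2). Baseline and demographic characteristics requires data-set sizes by group and reasons for termination, an emptied PPS would be noticed.

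Much of this stands as a limit on size. The intended meaning may well be harmless, the extent cannot be computed, and the FAS result is sound on either reading. It does not remove the point. The Protocol does not leave PPS membership to another document. It lists the conditions in full, and one of them, followed as written, excludes patients because they died. Noticing a depleted set afterwards does not repair it. A partial loss of deaths would be harder to see than a survival figure of 100%.

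**Conclusion.** The concern holds. The PPS rule as written selects on the primary event, and the main indicators are ordered to be analysed in that set. The effect ranges from none, if visits are counted only while the patient is alive, to complete loss of the day-28 comparison in the PPS, if the rule is applied literally and a visit falls at or after day 28. Where the truth lies between these depends on the visit schedule and on mortality, neither of which the Protocol gives. The harm is confined to the PPS analyses. It should be corrected, but it does not threaten the FAS result.

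**What to change.** Add to the PPS definition in item (2) 2): death counts as completed follow-up and is not by itself a reason for exclusion from the PPS; visit completion is assessed only up to the date of death. The other PPS conditions continue to apply to patients who die.

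The cost is one sentence. No new data are needed, because vital status is already required for the main indicators. The wording should be settled before PPS membership is decided at data review.

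### For the cost outcomes (and DDD, if measured per patient), choosing t test or Wilcoxon from the data in each centre does not lead to one mean-scale effect that the planned meta-analysis can pool

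*Protocol*

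**What the plan says.** Three statements in the protocol have to be read together.

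- **Choice of test.** Under Statistical analysis plan, General principles, the rule is: "quantitative data between groups will be based on the data distribution using group t test (homogeneity of variance, normal distribution) or Wilcoxon rank sum test". The t test needs both normality and equal variances; otherwise the rank test is used.
- **Level and pooling.** The last paragraph of Effectiveness analysis reads: "For all the outcome indicators, first conduct independent evaluation in each research center in accordance with general principles". It continues: "Then meta-analyze the research results of each research center". The general principles also announce the pooling: "The research results of each research center are evaluated by meta-analysis to evaluate the heterogeneity and the overall research merger effect". Neither place names an effect measure.
- **Outcomes concerned.** The secondary list includes "Total cost of living in ICU", "Total hospitalization expenses" and "DDD is used for antibiotics in hospital".

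Two further provisions bear on the point. The general principles have means, SDs, medians and quartiles described for every quantitative indicator. The effectiveness section closes with a mixed model, presented as an adjustment for bias, whose response scale is not stated.

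**The concern.** A t test goes with a difference in means. A rank-sum test comes with a P value and, at most, a statement about the probability that a patient on one regimen costs more than a patient on the other. If the choice is made from each centre's data, some centres may report the first and some the second, and these do not estimate the same quantity.

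The routing matters as well. Cost data are usually skewed, and the rule also sends unequal-variance data to Wilcoxon. Unequal spread is where a rank comparison and a mean comparison part most clearly. A patient-level total adds up to a budget through the arithmetic mean, so a reader of a cost result will usually take it as a statement about mean cost. A rank test may then signal a difference when mean cost is equal, or miss a difference that lies in the long-stay tail.

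**Working it through.** The protocol gives no cost figure, SD, sample size or number of centres, so there is no stated figure to reproduce. Everything below assumes lognormal costs and two-sided tests at raw P < 0.05. The protocol's own criterion is an adjusted Q value of at most 0.05.

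**1. Can centres end up with different tests?** Assume 10 centres, all drawn from one distribution with no regimen difference. The protocol names no pre-test, so assume that the t test is used only if Shapiro-Wilk in both arms and Levene all give P > 0.05. Let *f* be the simulated share of centres that use the t test. The chance that the 10 centres do not all use the same test is 1 − *f*¹⁰ − (1 − *f*)¹⁰.

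| Patients per arm | Log-SD | *f* | Chance of mixed tests |
|---|---|---|---|
| 15 | 0.6 | 0.22 | 92% |
| 15 | 0.8 | 0.074 | 54% (up to 59% in repeat runs) |
| 30 | 0.4 | 0.185 | 87% |
| 30 | 0.5 | 0.071 | 52% |
| 30 | 0.6 | 0.033 | 28% (19% in a repeat run) |
| 30 | 0.8 | about 0 | 0% to 3% |
| 60 | 0.5 | 0.001 | 1% |

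For example, 1 − 0.22¹⁰ − 0.78¹⁰ = 1 − 0.000 − 0.083 = 0.917. Mixing is likely in small or mildly skewed centres. In larger or strongly skewed centres it fades because nearly all use Wilcoxon.

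**2. Does the rank test follow mean cost?** With log-scale mean μ and SD σ, the mean cost is exp(μ + σ²/2), and P(X > Y) = Φ[(μ₁ − μ₀)/√(σ₁² + σ₀²)].

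- *Equal means, log-SD 0.8 and 1.0.* μ₁ − μ₀ = −0.32 + 0.50 = 0.18, so P(X > Y) = Φ(0.18/√1.64) = Φ(0.141) = 0.556. Wilcoxon rejects in about 40% of runs at 150 per arm. At 500 per arm it rejects in about 88%, against about 5% for Welch.
- *Equal medians, same log-SDs.* P(X > Y) = 0.5, yet the mean ratio is exp[(1.00 − 0.64)/2] = exp(0.18) = 1.197. At 500 per arm Wilcoxon rejects in about 5% of runs and Welch in about 67% to 69%.
- *Equal log-SD 0.8, common cost ratio 1.2.* At 500 per arm Wilcoxon rejects in about 94% of runs and Welch in about 87%. Here the rank test has more power.
- *Equal means at centre size.* In the first scenario Wilcoxon rejects in only about 7% of runs at 15 per arm and 12% at 30 per arm.

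The disagreement therefore depends on the regimens differing in spread, and it becomes large only in large comparisons.

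**The case against.** A reader might infer that the planned meta-analysis cannot be carried out. The protocol does not support that. Means and SDs are to be described, so each centre can supply a mean difference and standard error whatever test it reports, and nothing says that P values or rank statistics are what is pooled. Pooling mean differences from 10 simulated centres (30 per arm, log-SD 0.8, no difference) worked, with 5.3% rejection; under the unequal spreads used above, rejection was 9.6%. The closing mixed model could also give one estimate on a common scale.

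A reader might also infer that the plan contradicts a declared mean-cost outcome. It does not: the costs are listed as totals, which can be read as all charges for one patient, and no mean difference or budget aim is stated.

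Other points against the concern have force. The centre-level choice follows from reading two sections together. The baseline section uses the same pair of tests in a way that fits one choice per variable. Nothing in the protocol suggests that infusion duration changes the spread of costs. The DDD item does not say whether it is a per-patient quantity, and no separate calculation was made for it.

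What does not stand is that this is merely detail left to a separate analysis plan. The selection rule and the centre-by-centre step are stated choices, and a later plan could reach a common measure only by adding to or departing from them.

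**Conclusion.** The point holds in a limited form. The stated rule allows centres to be analysed by different tests. Where costs are skewed or variances unequal, it selects a test that gives no mean-cost effect to pool and may disagree with the mean-cost difference. A usable pooled result is attainable from other parts of the plan, but the rule does not lead to it.

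The size is uncertain. The chance of mixed tests runs from near 0% to over 90% across plausible skew and centre size. The disagreement between rank and mean results is large only if spread differs between regimens. All of this rests on assumed lognormal costs, assumed centre numbers and sizes, and an assumed pre-test. The two cost outcomes are affected, and DDD if it is measured per patient. The survival endpoints are not. The change is worth making but is not critical to the trial's main conclusion.

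**What to change.** For ICU cost, hospital cost and per-patient DDD, drop the distribution-based choice of test. Fix in advance one effect measure, the difference or the ratio of arithmetic means, with a confidence interval from an unequal-variance or generalised linear model method. Use the same measure in every centre, in the meta-analysis and in the final mixed model, which should contain regimen, phase and centre. State whether DDD is recorded per patient. Keep medians and quartiles as description, and keep any Wilcoxon test as a sensitivity analysis. Bootstrapping by centre and a breakdown of costs by survival status are not needed for this point.

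The cost is a change of wording and modest programming, with no new data. The downside is a possibly wider interval with a heavy tail, and less power than the rank test when the regimens differ by a common ratio (about 87% against 94% in the illustration).

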## 2). Baseline and demographic characteristics

Summarize the number of enrollment and make a list of dropped cases. The size of the data set in each group, the distribution of cases in each center, the comparison of the total dropout rate, and a detailed list of the reasons for termination.

The demographic characteristics (age, sex, height, body mass index, vital signs, etc.), history of allergies, etc. of the subjects were statistically described. According to the numerical characteristics of the variables, the t-test/Wilcoxon rank sum test was used to compare the quantitative data of the two groups of subjects such as age, height, and body mass index; the chi-square test/exact probability method was used to determine the gender of the subjects, post medical history, allergy history and other categorical variables for comparison.

Analysis of dropped cases: Cases that meet the criteria for dropped cases and the subjects withdrew from the study should be included in the dropped case analysis. The total dropout rate between groups and the dropout due to adverse events were compared using the chi-square test.

## 3). Effectiveness analysis

(1) Baseline index: Describe the baseline of each curative effect index, refer to general statistical methods for the comparison method between groups. A stratified analysis was performed

based on the subjects' SOFA score.

(2) Main efficacy indicators: The clinical efficacy is evaluated by the survival rate in the ICU and the survival rate on the 28th day after enrollment. Simultaneous FAS analysis and PPS analysis.

(3) Secondary curative effect index

- ① Stratified analysis of clinical effectiveness;
- ② Bacterial clearance rate;
- ③ Infection recurrence rate;
- ④ Isolation rate of new resistant bacteria;
- ⑤ Infection rate of newly emerging drug-resistant bacteria;
- ⑥ Total cost of living in ICU;
- ⑦ Total hospitalization expenses;
- ⑧ DDD is used for antibiotics in hospital.

For all the outcome indicators, first conduct independent evaluation in each research center in accordance with general principles. Then meta-analyze the research results of each research center. Assess the heterogeneity and the combined effect of the overall study. Finally, a multivariate stratified mixed model was used to adjust the potential bias.

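### Testing every outcome centre by centre first compares phases, not just regimens, so centre-level significance and heterogeneity findings can reflect phase variation alone

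*Protocol*

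**What the plan says.** In the Protocol's timetable (under the short-term infusion arm), centres are randomised to start on one regimen or the other and use it for everyone admitted in that phase. "Each research center is divided into 3 research phases", and "In the second research phase, each participating center automatically crosses into another program group". An individual patient's regimen is not randomised: "The dosing regimen of all enrolled cases is based on the group of the research center on the day of enrollment". The regimen of the third phase is not stated. Centres take part for at least a year "in order to cover the difference in the incidence of different pathogenic infections in different seasons throughout the year".

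Section 3), Effectiveness analysis, sets three steps: "For all the outcome indicators, first conduct independent evaluation in each research center in accordance with general principles"; then a meta-analysis of the centre results, covering heterogeneity and the combined effect; and last a mixed model to adjust for potential bias.

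The general principles in the Protocol's statistical analysis plan are the t or Wilcoxon test for quantitative data, log-rank and Cox for survival times, and, for categorical data, "The data uses the chi-square test or the exact probability method (if the chi-square test is not applicable". A Q value of at most 0.05 "will be considered as statistically significant (unless otherwise specified"). Neither the tests nor the heterogeneity step is given a phase or cluster term. The mixed model is directed at confounding between centres in treatment, service and management.

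**The concern.** Inside one centre the regimen changes only when the phase changes. With one phase per regimen, that centre's data cannot separate the two. With three phases there is at most one replicated phase. A patient-level chi-square or log-rank test treats the patients of a phase as independent draws, so anything that shifts outcomes in that phase (season, pathogen mix, staffing) is counted as evidence about the regimen. Centres on opposite sequences are pushed in opposite directions by a shared phase effect, and the heterogeneity test then sees this as disagreement about the regimen.

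The false discovery adjustment does not help, because it presumes valid p-values. A mixed model fitted afterwards does not repair centre results already declared significant or a heterogeneity statistic already computed from them. At stake is a report that the regimen works in some centres and not in others when only the phases differed.

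**Working it through.** The protocol has no figure to reproduce: no sample size, centre count, event rate or ICC. The inputs below are therefore assumptions: 30% mortality, m = 40 per centre-phase, 8 centres with half on each sequence, no regimen effect, and phase effects centred so that the mean logit is logit(0.30). ABA/BAB means the third phase returns to the first regimen; ABB/BAA means it repeats the second.

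**One centre, fixed phase effect.** With d the difference between regimen groups caused by phase alone, s0 the pooled and s1 the unpooled standard error, the rejection rate is 1 − Φ((1.96·s0 − |d|)/s1) + Φ((−1.96·s0 − |d|)/s1).

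- ABA, middle phase raised by OR 1.5 (log OR 0.405): mortality 27.2% in 80 patients against 36.0% in 40. d = 0.0872, s0 = 0.0889, s1 = 0.0907. Rejection = 1 − Φ(0.958) + Φ(−2.881) = 17.1%.
- ABA, OR 1.5 in phase 3 only: 31.6% against 27.2%, d = 0.0436; rejection 7.4%.
- ABA, linear trend reaching OR 1.5 by phase 3: phases 25.9%, 30.0%, 34.4%. Groups 30.2% against 30.0%, d = 0.0017; rejection 5.0%. The trend cancels.
- ABB, same trend: 25.9% against 32.2%, d = 0.0629; rejection 10.3%.
- Two phases only, OR 1.5: 25.9% against 34.4%, d = 0.085; rejection 13.0%.

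**One centre, random centre-by-phase variation.** With latent ICC ρ, half at centre-phase level, σ² = ½·(π²/3)·ρ/(1−ρ). The variance of the contrast is inflated by about 1 + m·p(1−p)·σ².

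- ρ = 0.05: σ² = 0.0866, inflation 1 + 40 × 0.21 × 0.0866 = 1.73; rejection 2(1 − Φ(1.96/√1.73)) = 13.6%.
- ρ = 0.02: σ² = 0.0336, inflation 1.28; rejection 8.3%.

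**Whole procedure by simulation** (4000 trials per row). This uses chi-square per centre, Benjamini–Hochberg across centres for one outcome (the protocol's FDT read as false discovery rate), and Cochran's Q on centre log odds ratios. Rejection in %, with no regimen effect:

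| Scenario | Single centre | Any centre after FDR | Heterogeneity |
|---|---|---|---|
| No variation | 5 | 5 | 4 |
| ABA, linear | 5 | 4 | 4 |
| ABA, phase 3 only | 7 | 7 | 8 |
| ABA, middle phase | 17 | 34 | 49 |
| ABA, ICC 0.02 | 8 | 12 | 11 |
| ABA, ICC 0.05 | 13 | 25 | 26 |
| ABA, middle phase and ICC 0.05 | 24 | 57 | 66 |
| ABB, linear | 10 | 13 | 17 |
| Two phases, OR 1.5 | 13 | 21 | 29 |

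With 20 centres the heterogeneity test rejects in 3% (linear), 10% (phase 3 only), 76% (middle phase) and 46% (ICC 0.05).

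Centre size matters. At 20 per centre-phase, ICC 0.02 gives 7% (single centre) and 6% (heterogeneity), and a middle-phase OR of 1.25 gives 7% and 9%. At 80 the same cases give 12% and 24%, and 12% and 30%.

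**Pooled test.** At 40 per centre-phase and 8 centres, random-effects pooling rejects in 1–7%. Fixed-effect pooling rejects in 3–5% with a common phase effect only and in 9–13% at ICC 0.05.

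**Other settings.** With 10 centres, 70% survival, 60 per centre-phase, ABA/BAB and a centre-by-phase SD of 0.3 on the logit scale (3000 trials), the single-centre test rejects in 17.8%, heterogeneity in 50.0%, fixed-effect pooling in 16.2% and random-effects pooling in 6.9%.

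**The case against.** The first step can be read as the first stage of a two-stage meta-analysis that merely supplies centre estimates; nothing makes one centre's significance a conclusion of the trial. The overall result comes from the later steps, and their details may sit in a statistical analysis plan that is not shown. The large figures need a chosen pattern. At the base setting a middle-phase OR of 1.25 gives only 8/13/16% (single centre, any after FDR, heterogeneity), and an ICC of 0.01 gives 7/8/8%. The two-phase rows depart from the stated three phases. The seasonal remark concerns which pathogens are seen, not mortality.

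Much of this stands as a limit on size and reach. The pooled estimate is not shown to be biased when sequences are balanced, and the pooling model and mixed-model terms are not faulted here. But the principles that govern the centre step are tests with a significance rule, and heterogeneity is to be assessed from their results. The protocol fixes this order itself, so no later choice of mixed-model terms undoes it. Milder assumptions shrink the error without removing its cause.

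**Conclusion.** The concern holds and should be corrected. Centre-level tests and the heterogeneity assessment are unreliable in three situations: random centre-by-phase variation; any phase difference if only two phases are compared; and, over three phases, a non-linear pattern under ABA/BAB or even a linear trend under ABB/BAA. A linear trend under ABA/BAB is harmless.

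Under the assumptions above, the error ranges from negligible to 24% for a single-centre test and 66% for heterogeneity with 8 centres. The mechanism is certain; its size in this trial is unknown.

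The overall conclusion is largely protected under random-effects pooling, at some cost in power. With 20 centres and a true OR of 0.7, a middle-phase OR of 1.5 lowers random-effects power from 95% to 83%, while a mixed model with a phase term stays at 97%.

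**What to change.** - Make the planned mixed model the primary analysis of the main survival endpoints: regimen and phase fixed, centre and centre-by-phase random. If centres are few, add a small-sample correction (t reference with within-centre degrees of freedom, or Kenward–Roger). A centre-phase summary analysis with centre and phase terms is an equivalent.
- State which regimen each sequence uses in the third phase, so that the phase term is defined.
- Show centre results descriptively, without significance tests.
- Assess heterogeneity of the regimen effect only in a model that contains centre-by-phase variation, as an estimate with an interval. With three phases this rests on the repeated-regimen phases alone; with two it cannot be separated.
- Keep any meta-analysis random-effects and supportive.

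In simulation under no effect (3000 trials, ABA), the mixed model rejects in 3.9–7.0% uncorrected and 2.2–4.9% with t on 13 df for 8 centres, and in 4.2–6.2% and 3.7–5.2% (37 df) for 20 centres.

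The cost is a rewritten analysis section. No new data are needed, and the named software can fit these models ("All statistical analysis is mainly conducted by SAS 9.4 and R 3.6.0"). Intervals widen where centre-phase variation is real. With 20 centres, ICC 0.05 and true OR 0.7, power is 81–83%, against an apparent 89–91% for fixed-effect pooling that rejects in about 12% under no effect. The valid heterogeneity test is weak: 12–19% power with 8 centres if the log OR varies between centres with SD 0.4.
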